4.1.5 Confirmation of Eligibility

Subject eligibility for enrollment will be assessed per [Section 3.3](#). All screening procedures, unless otherwise indicated, should be completed within 21 days of the first dose of study drug.

4.1.6 ECOG Performance Status

The ECOG performance index is provided in [Appendix 4](#).

4.1.7 Physical Examination, Vital Signs, Height, and Weight

The screening physical examination will include, at a minimum, the general appearance of the subject, height (screening only) and weight, and examination of the skin, eyes,

ears, nose, throat, lungs, heart, abdomen, extremities, musculoskeletal system, nervous system, and lymphatic system.

Symptom-directed physical exams will be done during the treatment period and at the treatment termination (TT) and safety follow-up (SFU) visits.

Vital signs (blood pressure, heart rate, and body temperature) will be assessed after the subject has rested in the sitting position.

4.1.8 Electrocardiogram

An ECG will be performed at screening. Subjects should be in a supine position and resting for at least 10 minutes before the ECG.

4.1.9 Urine or Serum Pregnancy Test

Pregnancy tests will be required only for women of childbearing potential. Testing will be done by a local or central laboratory as listed on the investigator's Form Food and Drug Administration (FDA) 1572.

4.1.10 Hematology

Hematology studies must include CBC with differential including, but not limited to white blood cell count, hemoglobin, hematocrit, platelet count, ANC, and absolute lymphocyte count (ALC). Cycle 1 Day 1 hematology does not need to be repeated if screening hematology was done within 10 days. Testing will be done by a local or central laboratory as listed on the investigator's Form FDA 1572.

4.1.11 Serum Chemistry

Chemistry will include albumin, alkaline phosphatase, ALT, AST, bicarbonate, BUN, calcium, chloride, creatinine, glucose, LDH, magnesium, phosphate/phosphorus, potassium, sodium, total bilirubin, total protein, and uric acid. Cycle 1 Day 1 serum chemistry does not need to be repeated if screening serum chemistry was within 10 days. If an unscheduled ECG is done at any time, then an electrolyte panel (i.e., calcium, magnesium, and potassium) must be done to coincide with the ECG testing. Testing will be done by a local or central laboratory as listed on the investigator's Form FDA 1572.

4.1.12 Coagulation

Coagulation studies must include PT and aPTT. Testing will be done by a local or central laboratory as listed on the investigator's Form FDA 1572.

4.1.13 Urinalysis

Urinalysis includes pH, ketones, specific gravity, bilirubin, protein, blood, and glucose. Testing will be done by a local or central laboratory as listed on the investigator's Form FDA 1572.

4.1.14 T/B/NK/Monocyte Cell Count

Flow cytometry testing will include cluster of differentiation (CD)3⁺, CD4⁺, CD8⁺, CD19⁺, CD14⁺ and CD16/56⁺ cells. Testing will be done by a local or central laboratory as listed on the investigator's Form FDA 1572.

4.1.15 Hepatitis B and C Testing

Hepatitis serology testing must include hepatitis B surface antigen (HBsAg), hepatitis B surface antibody (anti-HBs), anti-HBc, and hepatitis C (HCV) antibody. In addition, any subjects testing positive for any hepatitis serology, must have PCR testing during screening and on study (see [Appendix 1](#) and exclusion criterion #23). Testing will be done by local or central laboratory.

Subjects who are anti-HBc positive should have quantitative PCR testing for HBV DNA performed during screening and every 3 months thereafter. Regular monitoring (every 3 months) should continue until 12 months after last dose of study drug. Any subject with a rising viral load (above lower limit of detection) should discontinue study drug and have antiviral therapy instituted and a consultation with a physician with expertise in managing hepatitis B.

Subjects with a known history of hepatitis C or who are hepatitis C antibody positive, should be tested for HCV RNA, performed during screening.

Refer to [Section 3.9.4](#) and [Appendix 1](#) regarding monitoring of subjects who are anti-HBc positive or have a known history of HBV.

4.1.16 Pharmacodynamics/Pharmacokinetics and Biomarker Studies

CCI

CCI

For subjects who are receiving the EIAEDs carbamazepine or phenytoin, who are either enrolled in the Phase 1b portion or approved by the medical monitor to participate in this study: therapeutic drug monitoring for carbamazepine and/or phenytoin levels will be done (0) predose and 1 hour postdose on Cycle 1 Day 1, anytime during the visit on Cycle 1 Day 8, predose and 1 hour postdose on Cycle 1 Day 15 and Cycle 1 Day 22, then monthly thereafter and should be repeated after any dose change until sufficient data are available to discern whether time-dependent inhibition of CYP enzymes are or are not a concern. Therapeutic drug monitoring will be performed locally. Note: Under Amendment 2 of the protocol, subjects requiring EIAEDs are excluded.

CCI

4.1.17

CCI

CCI

4.1.18

CCI

CCI

CCI

4.1.19 Patient-Reported Outcome

CCI

CCI

4.1.20 Study Drug Accountability

See [Section 7.6](#).

4.2 INVESTIGATOR'S ASSESSMENT OF RESPONSE TO TREATMENT

Responses will be categorized as CR, PR, stable disease, or progressive disease. The definitions of response per the RANO criteria ([Wen 2010](#)) are provided in [Table 4-1](#).

Table 4-1. Criteria for Response Assessment

Response Category	Definition
CR	
Requires all of the following:
 
• Complete disappearance of all enhancing measurable and nonmeasurable disease sustained for at least 4 weeks• No new lesions• Stable or improved nonenhancing (T2/FLAIR) lesions• Patients must be off corticosteroids (or on physiologic replacement doses only)• Stable or improved clinically 
Note: Patients with nonmeasurable disease only cannot have a complete response; the best response possible is stable disease.

PR	
Requires all of the following:
 
• $\geq 50\%$ decrease compared with baseline in the sum of products of perpendicular diameters of all measurable enhancing lesions sustained for at least 4 weeks• No progression of nonmeasurable disease• No new lesions; stable or improved nonenhancing (T2/FLAIR) lesions on same or lower dose of corticosteroids compared with baseline scan• The corticosteroid dose at the time of the scan evaluation should be no greater than the dose at time of baseline scan• Stable or improved clinically 
Note: Patients with nonmeasurable disease only cannot have a partial response; the best response possible is stable disease.

SD	
Requires all of the following:
 
• Does not qualify for complete response, partial response, or progression• Stable nonenhancing (T2/FLAIR) lesions on same or lower dose of corticosteroids compared with baseline scan. 
In the event that the corticosteroid dose was increased for new symptoms and signs without confirmation of disease progression on neuroimaging, and subsequent follow-up imaging shows that this increase in corticosteroids was required because of disease progression, the last scan considered to show stable disease will be the scan obtained when the corticosteroid dose was equivalent to the baseline dose.

Table 4-1. Criteria for Response Assessment

Response Category	Definition
PD	Defined by any of the following: 
• $\geq 25\%$ increase in sum of the products of perpendicular diameters of enhancing lesions compared with the smallest tumor measurement obtained either at baseline (if no decrease) or best response, on stable or increasing doses of corticosteroids*• Significant increase in T2/FLAIR nonenhancing lesion on stable or increasing doses of corticosteroids compared with baseline scan or best response after initiation of therapy* not caused by comorbid events (e.g., radiation therapy, demyelination, ischemic injury, infection, seizures, postoperative changes, or other treatment effects)• Any new lesion• Clear clinical deterioration not attributable to other causes apart from the tumor (e.g., seizures, medication adverse effects, complications of therapy, cerebrovascular events, infection, and so on) or changes in corticosteroid dose• Failure to return for evaluation as a result of death or deteriorating condition• Clear progression of nonmeasurable disease

MRI=magnetic resonance imaging; FLAIR=fluid-attenuated inversion recovery.

NOTE: All measurable and nonmeasurable lesions must be assessed using the same techniques as at baseline.

*Stable doses of corticosteroids include patients not on corticosteroids.

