criteria, the SAC and the Safety Review Committee will review data after the 2nd interim analysis and will make a recommendation if study should be continued into Phase 2. If continued, up to 28 additional subjects may be enrolled for a total of 43 subjects on the 200-mg BID dose (15 subjects from Phase 1b and 28 subjects from Phase 2) in order to complete Phase 2. The final analysis will occur 24 weeks after the last subject is enrolled in the study. Treatment will continue until the last enrolled subject experiences disease progression.

Figure 3-1. Study Schema

*Note: Per Protocol Amendment #2, the Scientific Advisory Committee (SAC) observed that response and disease-control rate observed in the 200 mg BID cohort were numerically higher than in the 400 mg QD cohort. Therefore, the 400 mg QD cohort is discontinued.

**Note: Per Protocol Amendment #2, enzyme-inducing antiepileptic drugs (EIAEDs) are no longer considered the standard of care for patients with glioblastoma (Ref. NCCN guidelines version 1 2016). As a result, the requirement for subjects (4 subjects in the 200 mg BID cohort and 3 subjects in the 400 mg QD cohort to receive EIAEDs has been eliminated. One subject receiving EIAEDs has already been enrolled into the 400 mg QD cohort) and will continue to receive treatment per protocol.

BID = twice per day; CYP = cytochrome P450; EIAEDs = enzyme-inducing antiepileptic drugs; GBM = glioblastoma multiforme; ORR = overall response rate; QD = once per day.

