- s. Subjects who are anti-HBc positive (or have a known history of HBV infection) should have a quantitative PCR test for HBV DNA performed during screening and every 3 months thereafter. Regular monitoring (every 3 months) should continue until 12 months after last dose of acalabrutinib. Any subject with a rising viral load (above lower limit of detection) should discontinue acalabrutinib and have antiviral therapy instituted and a consultation with a physician with expertise in managing hepatitis B.

CCI

- v. Under Amendment 2 of the protocol, the SAC observed that the response and disease-control rate observed in the 200-mg BID cohort were numerically higher than in the 400-mg QD cohort. Therefore, the 400-mg QD cohort was discontinued.
- w. An MRI of the CNS must be performed at screening, on Cycle 3 Day 1, Cycle 4 Day 1 (4 weeks after Cycle 3 Day 1 scan to evaluate for response stability), then on Day 1 of every other cycle (every 8 weeks) thereafter (e.g., Cycle 6 Day 1, Cycle 8 Day 1); if symptomatic, then MRIs may be performed more frequently at investigator discretion.

CCI

- z. Concomitant medications of interest that will be collected throughout the study include corticosteroids and EIAEDs. Note: Under Amendment 2 of the protocol, no additional subjects on EIAEDs will be enrolled.

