Increase in corticosteroid dose alone, in the absence of clinical deterioration related to tumor, will not be used as a determinant of progression. Patients with stable imaging studies whose corticosteroid dose was increased for reasons other than clinical deterioration related to tumor do not qualify for stable disease or progression. They should be observed closely. If their corticosteroid dose can be reduced back to baseline, they will be considered as having stable disease; if further clinical deterioration related to tumor becomes apparent, they will be considered to have progression. The date of progression should be the first time point at which corticosteroid increase was necessary.

The definition of clinical deterioration is left to the discretion of the treating physician, but it is recommended that a decline in the KPS from 100 or 90 to 70 or less, a decline in KPS of at least 20 from 80 or less, or a decline in KPS from any baseline to 50 or less, for at least 7 days, be considered neurologic deterioration unless attributable to comorbid events or changes in corticosteroid dose. Similarly, a decline in the Eastern Cooperative Oncology Group and WHO performance scores from 0 or 1 to 2 or 2 to 3 would be considered neurologic deterioration.

Patients with nonmeasurable enhancing disease whose lesions have significantly increased in size and become measurable (minimal bidirectional diameter of ≥ 10 mm and visible on at least two axial slices that are preferably, at most, 5 mm apart with 0-mm skip) will also be considered to have experienced progression. The transition from a nonmeasurable lesion to a measurable lesion resulting in progression can theoretically occur with relatively small increases in tumor size (eg, a 9 × 9 mm lesion [nonmeasurable] increasing to a 10 × 11 mm lesion [measurable]). Ideally, the change should be significant (> 5 mm increase in maximal diameter or ≥ 25% increase in sum of the products of perpendicular diameters of enhancing lesions). In general, if there is doubt about whether the lesion has progressed, continued treatment and close follow-up evaluation will help clarify whether there is true progression.

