### **10.7.1 Best Overall Response, Disease Control Rate and Overall Response Rate per RANO criteria**

Measurable disease (bidimensional) as defined by the RANO criteria. RANO criteria (Wen 2010) will be followed for selection of measurable and non-measurable lesions and about the number of lesions to be assessed, as well as for the assessments of response and progression.

Disease Control Rate (DCR) is defined as the proportion of subjects who achieve a best response of SD, PR or CR at any point of the study.

Overall response Rate (ORR) is defined as the proportion of subjects who achieve a best response of PR or CR at any point of the study.

The primary analysis of DCR and ORR will be conducted using safety analysis set. DCR and ORR will be calculated with the corresponding exact binomial 2-sided 95% CI and 1-sided 90% CI (or 2-sided 80% CI) for treatment cohort.

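### SAP 10.7.1 counts stable disease towards the disease control rate with no minimum time from first dose, so stable disease on an early unscheduled MRI followed by progression counts as disease control.

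*Protocol*

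**What the plan says.** **Definition of DCR.** SAP 10.7.1 defines it as "the proportion of subjects who achieve a best response of SD, PR or CR at any point of the study". The denominator is the safety analysis set, meaning every subject who took any acalabrutinib (SAP 6.1). The estimate is reported beside ORR with exact confidence intervals. The section heading mentions best overall response, but no algorithm for it follows. The section also says that RANO governs the assessment of response and progression.

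**Scan timing.** Protocol Appendix 1, footnote w, schedules MRI at screening, Cycle 3 Day 1, Cycle 4 Day 1 and then every 8 weeks. It adds: "if symptomatic, then MRIs may be performed more frequently at investigator discretion".

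**Response categories.** Protocol 4.2 says: "Responses will be categorized as CR, PR, stable disease, or progressive disease". One requirement for SD in Table 4-1 is: "Stable nonenhancing (T2/FLAIR) lesions on same or lower dose of corticosteroids compared with baseline scan".

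**The in-between state.** Appendix 2 (RANO) says that subjects with stable imaging whose steroid dose was "increased for reasons other than clinical deterioration related to tumor do not qualify for stable disease or progression". It then gives a way out: "If their corticosteroid dose can be reduced back to baseline, they will be considered as having stable disease". If tumor-related deterioration follows instead, the subject is a progression.

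**The concern.** A disease control rate is meant to describe subjects whose tumor was held in check for some period. Here the numerator has no time element, so any post-baseline scan read as SD is enough. A subject scanned for symptoms at week 3, read as SD and then progressing at week 5, meets the SAP definition although the first scheduled assessment was never reached.

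The cohorts have 15 and 9 subjects, so one such classification visibly moves the percentage and its interval. A reader will set DCR beside ORR, because the SAP reports the two together.

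The second, smaller matter is that the four categories in section 4.2 cannot hold the steroid-increase state in Appendix 2. The plan does not say how a subject who never leaves that state enters DCR.

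**Working it through.** **1. The plan's own figure.** The only power figure concerns ORR: 43 subjects, 5% against 20%, one-sided exact test at 0.025, about 88% power (Protocol 5.1, SAP 3.2). The smallest qualifying cut-off is 6 responders of 43:
- P(X ≥ 6 | 43, 0.05) = 0.0194
- P(X ≥ 6 | 43, 0.20) = 0.8855

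The stated power is reproduced. It does not depend on how SD is counted. The documents state no DCR figure.

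**2. Earliest scheduled SD.** Protocol 5.1 equates 2 cycles with 8 weeks, so a cycle is 28 days.
- Cycle 3 Day 1 = 2 × 28 + 1 = Day 57.
- The visit window is ±3 days, so the earliest scheduled scan is Day 54.
- With first dose on Day 1, Day 54 is 54 − 1 = 53 days after first dose, and 53 / 7 = 7.6 weeks.

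SD from a scheduled scan therefore already implies about 7.6 to 8 weeks. Only an unscheduled MRI under footnote w can give SD sooner.

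**3. Weight of one subject.** Cohort sizes are in SAP 3.2. Each subject counted on an early SD read alone adds 1/n:

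| Such subjects | n=15 (200 mg BID) | n=9 (400 mg QD) |
|---|---|---|
| 1 | 1/15 = 6.7 points | 1/9 = 11.1 points |
| 2 | 2/15 = 13.3 points | 2/9 = 22.2 points |

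**4. Illustration with assumed counts** (exact two-sided 95% intervals). Removing one subject gives:
- n=15: 9/15 = 60.0% (32.3 to 83.7) becomes 8/15 = 53.3% (26.6 to 78.7).
- n=9: 5/9 = 55.6% (21.2 to 86.3) becomes 4/9 = 44.4% (13.7 to 78.8).

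**5. The category gap.** Take stable imaging with a steroid increase unrelated to tumor deterioration.
- SD fails, because Table 4-1 requires a dose no higher than at the baseline scan.
- PD fails, because Appendix 2 does not accept a steroid increase alone as progression.
- CR and PR do not apply to stable imaging.

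No listed category fits. For a subject who never resolves, a PD or blank entry and a not-evaluable entry all leave the subject out of the numerator over the same denominator. Only an SD entry, which the criteria bar, would raise DCR. A PD entry for a subject whose steroid dose later returned to baseline would lower it.

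**The case against.** **The early-SD route is narrow.** The narrative RANO text in Appendix 2 requires clinical stability for SD, and footnote w permits extra scans for symptoms. If an early scan is equivocal and progression follows, Appendix 2 dates the progression back to that scan, which then is not SD. The RANO text also sets no minimum SD duration, so the SAP does not depart from its source. This stands as to frequency, but it does not close the route. Table 4-1's SD row omits the clinical-stability condition, and its PD row excludes deterioration from causes such as seizures. A symptomatic subject with an unequivocally unchanged scan can therefore be read as SD.

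**DCR carries little weight.** It is not an objective or a listed endpoint (Protocol 3.1.3, SAP 4.2), and SAP 5 tests no hypothesis. The numerical criterion for Phase 2 was ORR. This stands, and it limits the point to a descriptive summary.

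**Readings the documents do not support:**
- *That the missing category forces sites to enter SD or PD, and so inflates DCR or shifts PFS dates.* The response eCRF is not among the documents. Table 4-1 and the SAP's adoption of RANO bar an SD entry. Protocol 5.4.4 and SAP 12.3 already allow for assessments that cannot be used. The category gap is a matter for clarification.
- *That this definition led to the dropping of 400 mg QD.* The Figure 3-1 note does say that "response and disease-control rate observed in the 200 mg BID cohort were numerically higher than in the 400 mg QD cohort". That decision followed the first interim analysis, however, while this SAP covers the final analysis. Elsewhere Protocol 3.0 and 3.2 attribute the decision to response, and no document gives the DCR definition used at the time.

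**Conclusion.** The concern holds in a limited form. As written, SAP 10.7.1 would count SD on an unscheduled MRI before the first scheduled scan as disease control even when progression follows. A missing minimum time can only add subjects to the numerator, so on this point DCR can be overstated but not understated. Each such subject is worth 6.7 points at n=15 or 11.1 points at n=9.

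That DCR actually is inflated is not shown. The documents report no DCR counts, no number of early scans and no number of steroid increases. The per-subject figures are simply 1/n, and the illustrated rates use assumed counts. The conclusion assumes only that at least one subject could have an early unscheduled SD read with no later qualifying scan.

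ORR, its 4-week confirmation and the power calculation are untouched. This is an inexpensive improvement to a secondary descriptive summary.

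**What to change.** **SAP 10.7.1, one sentence.** Count SD towards DCR only when it is shown on a scan at least 53 days after first dose (Day 57 less the 3-day window). Confirmed CR and PR count as now. An unconfirmed response that Appendix 2 downgrades to SD follows the same 53-day rule.

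**Clarification to Protocol 4.2 and SAP 10.7.1.** Reconcile the four categories with Appendix 2. Record a timepoint that is neither SD nor PD as not evaluable, and count it as not controlled for DCR unless it later resolves to SD under Appendix 2.

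**Cost.** The SD rule uses scan dates already collected and needs no new assessment. The clarification needs a not-evaluable response option if the eCRF lacks one, and one further SAP sentence. The downside is that DCR may be slightly lower. In particular, a subject whose only on-study scan falls before Day 54 would count as not controlled even if the tumor was stable.

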4.3 TREATMENT TERMINATION AND SAFETY FOLLOW-UP VISITS

A TT visit is required for safety assessments for any subjects who permanently discontinue study drug for any reason (except for death, lost to follow-up, or withdrawal of consent), including disease progression. The TT visit should be scheduled within 7 days of the last dose of study drug, if possible, and is not required for subjects who discontinue from the study treatment within 10 days of a scheduled study visit or if the TT visit would be performed within 14 days of the SFU visit.

In addition to the TT visit, each subject should be followed until the SFU visit at 30 (+7) days after his or her last dose of study drug to monitor for resolution or progression of AEs and to document the occurrence of any new events, regardless of whether the subject receives a new anticancer therapy or demonstrates disease progression within this timeframe. Subjects who withdraw consent for study treatment should still be encouraged to complete the SFU assessments, but these assessments cannot be mandated if subject consent for further study participation is withdrawn. If the TT visit and the SFU visit coincide, then these can be combined into 1 visit. The Schedule of Assessments ([Appendix 1](#)) describes the procedures required for the TT and SFU visits.

4.4 FOLLOW-UP FOR PROGRESSION AND SURVIVAL

4.4.1 Post-Treatment Disease Follow-Up

Each subject should be followed until disease progression or the start of alternative anticancer therapy. If neither of these has occurred at the time of the 30-day SFU visit, Post-Treatment Disease Follow-Up visits should occur approximately every 3 months (12 weeks) from the date of last dose until disease progression or next anticancer treatment. During this period, subjects will be followed via MRIs per investigator discretion.

